5.1 Design

We will conduct a pilot two-arm randomized, controlled trial comparing the effect of an online BWL program (intervention) to usual care on weight loss after 16 weeks. The enrollment process and intervention will all be conducted remotely. All interested participants will be asked to complete a 7-day run-in period during which time they will complete surveys and submit a daily food log. Participants will be randomized 2:1 into the intervention and control arms, respectively. At the end of the 16-week intervention, participants will be asked to complete end-of-study surveys and complete an end-of-study virtual weigh-in.

Study population

We will recruit women who have recently delivered at the Hospital of the University of Pennsylvania or Pennsylvania Hospital. We will recruit women who are 6 weeks – 12 months postpartum at the time of study recruitment and have ≥ 1 CV risk factor.

Trial arms

Arm 1. Usual care: Participants will receive educational resources on weight loss and a digital scale.

Arm 2. Online behavioral weight loss: Participants will receive educational resources on weight loss and a digital scale. Participants will participate in a “Weight Loss 101” virtual session, where they are introduced to successful components of weight loss. They will be enrolled in a 16-week online program that is based on the Diabetes Prevention Program (DPP) and involves weekly brief videos, a self-monitoring platform, and automated feedback.(3,6–8)

Intervention

Participants in all arms will attend a virtual Information session, undergo a 1-week behavioral run-in period, and attend a virtual Kick-off session. (see Study Schema). After completing these steps, all participants will be asked to complete a virtual weigh-in at the start and end of the 16-week intervention. In addition, the intervention arm will receive:

- a. Weight loss and physical activity goals as part of the Weight Loss 101 session. All participants will be asked to lose 10% of their body weight, corresponding to 1-2 lb/week over the 16-week study. Participants will be enrolled in the online behavioral weight loss program. The program involves the following components and described in more detail in Appendix 1:
- b. Weekly multimedia videos (lesson plan): These illustrated videos are < 5 minutes in length and include topics such as stimulus control, goal setting, and problem solving.

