5.5 Key inclusion criteria

- 1) Age ≥ 18 years;
- 2) Delivered a baby at HUP or PAH within 8 weeks-12 months prior to study enrollment;
- 3) $BMI \geq 27$ kg/m^2

- 4) Diagnosis of one of the following medical conditions: chronic hypertension, gestational hypertension, preeclampsia, eclampsia, gestational diabetes, or diabetes mellitus (type 1 or 2) based on diagnosis codes in the EMR
- 5) Has online access through smartphone or computer and has email address
- 6) Ability to read and provide informed consent to participate in the study

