5.6 Key exclusion criteria

- 1) Delivered prior to 32 weeks gestation in the EMR
- 2) Documentation of fetal demise or neonatal demise in the EMR
- 3) Currently pregnant or planning to get pregnant within the next 5 months
- 4) Does not speak English
- 5) Answers yes to any of the following questions:
 - Are you currently participating in any other weight loss or physical activity studies?
 - Do you have any medical conditions or other reasons why you could not participate in a 16-week weight loss or physical activity program?
- 6) Participants will be excluded after completing the run-in period if they do not complete the daily food log or their baseline BMI is $< 27 \text{ kg/m}^2$

6. Subject recruitment

We will use EPIC to identify a cross-sectional cohort of potentially eligible patients. Given the lag time between identifying potentially eligible patients and enrollment, we will identify women with a delivery occurring between the time of the data pull and 365 days prior. We will identify women based on the inclusion and exclusion criteria above. In order to optimally recruit women with a $\text{BMI} \geq 27 \text{ kg/m}^2$ at time of enrollment, we will use the following BMI criteria as documented in EMR:

- a. Pregravid $\text{BMI} \geq 30$, regardless of delivery BMI
- b. Pregravid $\text{BMI} 28-29.9$ and delivery $\text{BMI} \geq 33$
- c. If pregravid BMI missing, will include delivery $\text{BMI} \geq 33$

Potentially eligible patients will have their current address, phone number, email address, demographics, and clinical history abstracted. We will compare two approaches to patient recruitment (see study schema above, enrollment strategies)

- a. Email: For patients meeting inclusion criteria with a documented email address, we will randomize them to one of two recruitment emails that test behavioral approaches to engaging patients. Group 1 (reserved a spot) will receive an email notifying them that we reserved a spot for them in the upcoming online information session for a weight loss program designed for postpartum women. Group 2 (commit today) will receive an email asking participants if they are ready to commit to their health. Participants will be able to click on an embedded link in the email which will take them to a secure Redcap survey that will allow them to sign up for the virtual information session. Once participants sign up, they will receive a text reminder prior to the information session with the Zoom link. See

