Appendix 2 for text of recruitment emails. For participants who do not respond, a reminder email will be sent 48 hours after the initial email.

- b. Mailer: We will combine participants who received an email but did not respond and patients who do not have an email address documented in the EMR. We will then randomize them to one of two mailer strategies: study mailer alone versus mailer plus gift. The mailer alone group will receive a flyer and mailer that focuses on achieving a healthy lifestyle postpartum and explaining the weight loss study (see Appendices 3 and 4). The mailer plus gift group will receive a mailed package containing the flyer and mailer plus a baby bib inscribed with study logo. Recruitment materials will be sent in waves until the expected number of participants are enrolled.

Patients will be able to sign up for the virtual information session hosted on Zoom through the study website (Redcap). Information on how to sign-up will be included on the mailer. In addition, patients will be able to call or text the study phone number to talk to a clinical research coordinator (CRC) in the Maternal and Child Health Research Center (MCHRC) to learn more about the study and/or sign up for an information session. We will try to accommodate patients who cannot make any of the scheduled sessions by scheduling additional sessions. In order to sign up, participants will need to provide their name, contact information, and date of birth.

As of 9/25/2021, we have reached target randomization using email recruitment alone. In order to compare the mailer versus mailer plus baby gift as outlined in Aim 2, we will continue recruitment using the mail strategy (see Study Schema, enrollment strategies above). When participants click on the Redcap link to sign up for a virtual information session, they will be informed that study enrollment is full. They will have the option to watch a 10-15 minute recorded video of study staff reviewing evidence based approaches to weight loss, which will be posted on the Recap website.

7. Subject compensation

All eligible participants will receive a scale if they complete the 1-week behavioral run-in period. Participants will receive \$30 after completing the 16-week intervention, virtual weigh-in and exit survey at the end of the study. Compensation will be delivered via Greenphire ClinCard.

8. Study procedures

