8.2 Procedures

- a) Virtual information session: All potentially eligible and interested participants will first complete this session. At the end of the session, participants will provide verbal informed consent and will be invited to complete the behavioral run-in period.
- b) Behavioral run-in: participants will be emailed a link to a secure Redcap survey and asked to complete the following steps:
 - Electronic consent
 - Survey to determine eligibility
 - Profile with contact information, including correct address to send scale and contact preferences (email or text)
 - Online W9 form to facilitate delivery of incentives
 - Baseline demographic and study specific surveys (see Appendix 5)

Participants will be asked to complete 5 days of food logging. Participants can log food in MyFitnessPal (MFP), a free app for food tracking, and share with research staff or they can keep a food diary on paper and send in screenshots via text or email. Participants who provide informed consent and complete the run-in period will be sent a digital scale along with handouts in preparation for the virtual kick-off session.

- c) Virtual kick-off session: Once participants have received the scale, they will be eligible to sign up for a virtual kick-off session, during which participants will be randomized. Participants can sign up through the study website (via Redcap) or by contacting a CRC. This session will be conducted by research staff over Zoom. Randomization will occur at the beginning of the session and participants will be placed in one of two breakout rooms for the intervention or control arm.

- Control arm: study staff member will inform participants that they are in the control arm.

- Intervention arm: study staff will lead the Weight Loss 101 session. This session will review weight, calorie, and physical activity goals and evidence-based weight loss strategies, including food logging and daily weights. All participants will be asked to lose 10% of their body weight, corresponding to 1-2 lb/week over the 16-week study. Participants will receive a brief introduction to the online BWL study website. The session will also include information about weight loss and exercise while breastfeeding.

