To compare sample characteristics between arms we will use t-tests or Wilcoxon rank-sum tests for continuous variables and Pearson chi square tests or Fisher's exact tests for categorical variables. Generalized linear mixed effects models will be used to assess for differences in weight, given repeated observations. We will use fixed effects to adjust for study arm, baseline weight, and calendar month, which may reflect seasonal variations that make weight loss harder or easier. We will conduct a number of sensitivity analyses to evaluate the robustness of our findings. All hypothesis tests will be two-sided using a two-sided alpha of 0.05 as our threshold for statistical significance. We will use Stata and/or SAS to analyze the data. We will use multiple imputation for missing data.

10. Investigators

[name], MPH is the co-Principal Investigator (PI) and is an Assistant Professor of Medicine at the Perelman School of Medicine. She is Director of the Women's Cardiovascular Health Program. She has experience running lifestyle interventions among postpartum women.

[name] is the co-Principal Investigator (PI) and is a Professor of Psychology in Psychiatry at the Perelman School of Medicine. She is Director of the Center for Weight and Eating Disorders. She has extensive experience designing and running behavioral weight loss clinical trials.

[name] is a co-investigator. She is Associate Professor in the Department of Allied Health Sciences and Co-Director of the Weight Management Research Group at the University of Connecticut (UConn). She developed the online BWL platform along with collaborators at the University of North Carolina.

The Clinical Research Coordinator has experience with administering studies involving interventions with pregnant and postpartum populations and also has experience training Research Assistants to follow study protocols.

11. Human research protection

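### Time since delivery is left out of the primary weight model: not a validity error, but one pre-specified linear term could buy some precision at little cost

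*Combined protocol and SAP*

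**What the plan says.** Section 9 plans mixed-effects models for weight and fixes the adjustment: "We will use fixed effects to adjust for study arm, baseline weight, and calendar month". Calendar month is included because of seasonal effects, "which may reflect seasonal variations that make weight loss harder or easier". The section also states "We will use multiple imputation for missing data" and promises sensitivity analyses without naming any.

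On entry timing, Section 5.5 requires "Delivered a baby at HUP or PAH within 8 weeks-12 months prior to study enrollment". Section 5.1 sets the upper limit at "12 months postpartum at the time of study recruitment" but starts the window at 6 weeks, so the two lower bounds need to be reconciled. Delivery timing is already used to build the cohort: in Section 6, "we will identify women with a delivery occurring between the time of the data pull and 365 days prior".

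Section 5.4 plans 60 women, 40 in the intervention arm and 20 in usual care. Section 8.2 says when allocation happens, "Randomization will occur at the beginning of the session and participants will be placed in one of two breakout rooms", and no section describes stratification. Section 6 reports "As of 9/25/2021, we have reached target randomization using email recruitment alone".

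**The concern.** The entry window covers about 44 weeks of the first postpartum year. Two women with the same baseline weight in the same month may be 2 and 11 months from delivery. The plan itself expects weight to move after birth: Section 6 uses separate pre-pregnancy and delivery BMI cut-offs to predict BMI at enrollment. If weeks since delivery predict the next 16 weeks of weight change beyond baseline weight and month, leaving them out has two consequences. The interval for the arm difference is wider than it need be, and a trial that happens to be unbalanced on timing has a shifted estimate that the model does not correct. Calendar month was admitted on an equally conditional rationale. With 60 women, precision is scarce.

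**Working it through.** The plan gives no SD, effect size, power or dropout, so it has no precision figure to reproduce. Its one derived count, about 1,200 eligible women, follows from 8,400 × 0.30 × 0.60 × 0.80 = 1,209.6 but does not bear on this point.

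**Inputs from the documents.** 40 vs 20 women (Section 5.4); two-sided alpha 0.05 (Section 9); a baseline and a final weigh-in for every participant (Section 8.2), so with baseline weight as a covariate each woman contributes one follow-up weight.

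**Assumptions.** The partial R² of time since delivery, given the listed covariates, is shown from 0 to 20%. Month uses 1 df (single term) or 11 df (categorical), as the plan does not say which. Reference power is 80%.

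**Step 1: interval width.** With month at 1 df the present model has 4 parameters and residual df 60 − 4 = 56, falling to 55 with the new term. With month at 11 df it has 14 parameters and residual df 46, falling to 45. The width ratio, adjusted to unadjusted, is approximately √[(1 − R²) × df before / df after]. For example, at R² = 10% with month at 1 df, √(0.90 × 56/55) = 0.957. Power is by noncentral t.

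| Partial R² | Width ratio, month 1 df | Width ratio, month 11 df | Power, 1 df | Power, 11 df |
|---|---|---|---|---|
| 0 | 1.009 | 1.011 | 79.3% | 79.1% |
| 5% | 0.984 | 0.985 | 81.3% | 81.1% |
| 10% | 0.957 | 0.959 | 83.3% | 83.1% |
| 20% | 0.903 | 0.904 | 87.4% | 87.2% |

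Simulated mean ratios agree: 1.010, 0.984, 0.958, 0.903 (1 df) and 1.012, 0.986, 0.960, 0.905 (11 df). If 20% of final weights are missing (an assumption; 32 vs 16, month 1 df), they are 1.012, 0.987, 0.960 and 0.905.

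**Step 2: break-even.** The term pays for itself when R² exceeds 1 − 55/56 = 1.8%, or 1 − 45/46 = 2.2%.

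**Step 3: how often a single trial gains.** At R² = 5% the adjusted interval is the narrower one in about 63% of simulated trials with month at 1 df and about 57% with month at 11 df. With month at 1 df the share is 20% at R² = 0, 84% at 10% and 98% at 20%.

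**Step 4: validity.** With the covariate omitted and no arm effect, simulated overall type I error is 5.0% at R² of 5%, 10% and 20%, and the mean estimate is about zero.

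**Step 5: chance imbalance (illustration).** Assume entry is uniform over 8–52 weeks. The SD is 44/√12 = 12.70 weeks, and the SE of the difference in arm means is 12.70 × √(1/40 + 1/20) = 3.48 weeks. A gap above 4 weeks (an arbitrary cut) then occurs in about 25% of trials. With month at 1 df, unadjusted type I error in those trials is 6.1%, 7.1% and 9.0% at R² of 5%, 10% and 20%. In the other 75% it is 4.6%, 4.4% and 3.6%. At R² = 20% these average to 0.25 × 9.0 + 0.75 × 3.6 = 4.95%, in line with Step 4. With month at 11 df the figures are milder: 5.8%, 6.7% and 8.1% with the gap, and 4.7%, 4.4% and 4.1% without. Adjusted (month 1 df), the rate is about 5% in both groups.

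**The case against.** The strongest reply is that nothing in the documents shows that this covariate matters once baseline weight and month are in the model. They do not rank it above other recorded candidates such as pre-pregnancy BMI or type of risk condition. The trial calls itself a pilot and states no power target, and at R² of 5% the gain is under 2% of interval width. This stands, and it is why the point is optional.

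The calculation also uses one follow-up weight per woman in a linear model, whereas Section 9 names mixed models for repeated observations. The two weigh-ins asked of everyone make that reasonable, but the percentages are approximate for the planned model.

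The comparison of characteristics between arms and the unnamed sensitivity analyses in Section 9 could bring an imbalance to light. Neither adjusts the primary estimate or commits to this term.

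A reader might infer three stronger things that the documents do not support:

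- That the omission biases the result or inflates type I error. Step 4 shows that it does not; the rates in Step 5 apply only to a subset of trials chosen by the size of the gap, and are offset in the rest.
- That model adjustment is the only way left to handle imbalance because randomization is complete. Section 8.2 describes when allocation occurs, not how the sequence was made, so silence about stratification does not show that there was none.
- That the difference between the 20-week study and the 16-week program (Section 5.2) makes the choice of reference date critical. A constant lag cannot change the fit of a linear term or the arm estimate, and the documents give no between-woman variation in that lag.

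**Conclusion.** The omission is real, and it is a matter of efficiency. The present model gives a valid randomized comparison. Adding time since delivery would change the interval by between about +1% (no prognostic value) and −10% (partial R² of 20%), and would help on average once R² exceeds about 2%. Those sizes rest on an R² range that is assumed, on the linear one-follow-up model, and on 40 vs 20 women. The imbalance figures further assume uniform entry and a 4-week cut. The point is worth considering because the value is already held and the downside is small. The plan is not deficient without it.

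**What to change.** Before any outcome is compared between arms, add weeks since delivery, at a fixed reference date such as randomization, as one linear fixed effect in the primary weight-change model beside baseline weight and month. Put the same term in the imputation model, and report the present Section 9 model as a named sensitivity analysis.

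The deadline must cover comparisons by coded arm. Section 11.6.1 keeps the code letters until analysis is complete, and a 40/20 split shows which letter is which. Target randomization was reached by 9/25/2021, so outcomes may already have been examined. If they have been compared by arm, keep the Section 9 model as primary and label the adjusted model post hoc.

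Reconcile the 6-week and 8-week lower bounds in Sections 5.1 and 5.5.

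The cost is one line in the plan, one date subtraction and one degree of freedom. If the term has no prognostic value, the interval is about 1% wider and power falls by 0.7 to 0.9 points from an assumed 80%. A single linear term is a simplification, since the documents do not give the shape of the relation. The change covers weight change only, not the proportion losing at least 5%.

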11.1 Data confidentiality

Participants who are randomized into the online BWL program will be enrolled in the platform using the contact information (name, email address, and phone number) provided at the beginning of the study. The platform was designed by [name] (co-I) and collaborators and is being provided to the Penn study team to use as part of the study at no cost. Research staff working with [name] at UConn will be responsible for enrolling participants into the platform. Penn study staff will be provided a login and password to securely access any data entered into the platform by Penn participants. Penn study staff will not be able to enroll participants directly into the platform because this requires an administrator account, which would permit access to all studies that are ongoing within the platform at UConn. The participant information needed for enrollment (name, email, and phone number) will be

securely shared with the UConn research staff via a Penn Box link. Paper-based records will be kept in a secure location and only be accessible to personnel involved in the study. Computer-based files will only be made available to personnel involved in the study through the use of access privileges and passwords. Wherever feasible, identifiers will be removed from study-related information. Precautions are in place to ensure the data are secure by using passwords and encryption, because the research involves web-based surveys.

11.2 Subject confidentiality

Research material will be obtained from participant surveys and clinical data abstracted from the EMR. All participants will provide informed consent for access to these materials. The data to be collected include demographic data (e.g., age, sex, self-identified race) and outcome data. Research material that is obtained will be used for research purposes only. The same procedure used for the analysis of automated data sources to ensure protection of patient information will be used for the survey data, in that patient identifiers will be used only for linkage purposes or to contact patients. The study identification number, and not other identifying information, will be used on all data collection instruments. All study staff will be reminded to appreciate the confidential nature of the data collected and contained in these databases.

11.3 Subject privacy

Enrollment will include a description of the voluntary nature of participation, the study procedures, risks and potential benefits in detail. The enrollment procedure will provide the opportunity for potential participants to ask questions and review the consent form information with family and friends prior to making a decision to participate. Participants will be told that they do not have to answer any questions if they do not wish and can drop out of the study at any time, without affecting their medical care or the cost of their care. They will be told that they may or may not benefit directly from the study and that all information will be kept strictly confidential, except as required by law. Subjects will be given a copy of the consent document. All efforts will be made by study staff to ensure subject privacy.

